### **Study population**

The Consolidated Standards of Reporting Trials (CONSORT) checklist was used for the enrolment and allocation of patients. Children aged between two months and six years who were undergoing infra-umbilical surgeries with ASA PS I were randomly allocated to either group A (GA with CEB) or to group B (GA without CEB)., Both groups were compared based on hemodynamic stability, level of sedation, analgesia need, pain score, and parental satisfaction. Postoperative pain was evaluated by the Children's Hospital Eastern Ontario Pain Scale (CHEOPS), Faces Pain Scale-Revised (FPS-R), and Face, Legs, Activity, Cry CONSOL ability (FLACC) scales

The raw data which was collected from case report forms were entered into a Microsoft Excel Spreadsheet initially. Then, the data have been transferred to and analyzed by IBM SPSS Statistics software version 21. The categorical and numerical variables of both groups were analyzed and compared. Data are expressed as  $n$  (%), mean  $\pm$  standard deviation or median and interquartile range (IQR) according to distribution normality. Continuous variables were compared using the Mann-Whitney U test, and categorical variables were compared using Fisher's exact test or Pearson Chi-square test.  $P < 0.05$  was considered statistically significant. The confidence interval was set at 95%.

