## Tables and Figure legends

**Table 1.** Demographic parameters of children with (group A) or without (group B) caudal block anesthesia.

[figure not shown]
Demographic parameters	Group A (n=36)	Group B (n=36)	P
Age (months), mean $\pm$ SD	20.68 $\pm$ 1.7	29,688 $\pm$ 3.4	0.3
Sex			
Female	16 (13%)	15 (11.25%)	0.5
Male	20 (15%)	21(15.75%)	
Heights (cm), mean $\pm$ SD	90 $\pm$ 2.08	103 $\pm$ 4,2	0.8
Weights (kg), mean $\pm$ SD	9 $\pm$ 1,05	12 $\pm$ 3,02	0.6

SD= standard deviation.

[figure not shown]
**Table 2.** Differences between children with or without caudal block anesthesia in the average pain scores at the various time points according to Children's Hospital Eastern Ontario Pain Scale (CHEOPS).

Variables	Group A (n=36)	Group B (n=36)	P
CHEOPS Score average	3 $\pm$ 0.11	5 $\pm$ 0.49	<0.005
At 30 minutes	2.6 $\pm$ 0.41	4 $\pm$ 0.44	<0.003
At 1 hour	2.11 $\pm$ 0.98	4 $\pm$ 0.54	<0.0001
At 2 hours	3 $\pm$ 0.44	4 $\pm$ 0.65	<0.003
At 6 hours	3.05 $\pm$ 1.53	4.80 $\pm$ 2.04	0.005

Postoperative analgesia	Yes	3.0 (8.3%)	36 (100%)	<0.001
	No	33 (91.7%)	0.0 (0.0%)	
Parental satisfaction	Good	30 (80%)	5.0 (20%)	<0.002
	Perfect	30 (80%)	5.0 (20%)	<0.001

**Figure 1.** Effect of caudal block versus non-caudal block anesthesia on pain intensity at 1 and 6 hours and the degree of sedation in children undergoing infra-umbilical surgery under general anesthesia.

**Figure 2.** Effect of caudal block versus non-caudal block anesthesia on movement score at 1 and 6 hours postoperatively in children undergoing infra-umbilical surgery under general anesthesia.

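### Parental satisfaction is graded, but the SAP names only unordered tests for categories, Table 2 gives one P-value per grade, and the printed grade counts are impossible

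*SAP*

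**What the plan says.** The SAP's Study population section lists the outcomes compared between groups: "hemodynamic stability, level of sedation, analgesia need, pain score, and parental satisfaction". It then gives two rules. For categories: Fisher's "exact test or Pearson Chi-square test". For measurements: "Continuous variables were compared using the Mann-Whitney U test". No test for ordered categories is named, and the section does not say which rule covers satisfaction or sedation. A P-value below 0.05 "was considered statistically significant"; no multiplicity rule appears in the text available.

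In the SAP's Table 2, "Parental satisfaction" has two rows, reported as n (%), which puts it on the categorical side:

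| Grade | Group A (n=36) | Group B (n=36) | P |
|---|---|---|---|
| Good | 30 (80%) | 5 (20%) | <0.002 |
| Perfect | 30 (80%) | 5 (20%) | <0.001 |

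Just above, postoperative analgesia (yes or no) has one P-value for both of its levels. The protocol abstract gives a single satisfaction comparison: 92.1% v 63.9%, P=0.012.

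Sedation appears as an outcome name and in the Figure 1 legend, as "the degree of sedation in children undergoing infra-umbilical surgery under general anesthesia". No scale, levels, counts or test are given for it.

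**The concern.** Good and Perfect are answers to one question, so a parent can be in only one row. If the block moves parents from Good to Perfect, the Good row falls while satisfaction rises. A P-value for that row then does not say whether satisfaction went up or down. With three P-values for one outcome, the reader also cannot tell which is the trial's answer.

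A Fisher or Pearson test on the whole grade table avoids the row problem but spreads its power over every pattern of difference, including patterns that are not a shift. With 36 per arm, that can cost enough power to matter when there are three or more grades.

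The choice of test aside, the two printed rows do not look like a possible set of answers from 36 families per group.

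**Working it through.** **1. The printed counts.** Inputs: Table 2, 36 per group.
- Sum in group A: 30 + 30 = 60, against 36 children.
- Percentages: 30/36 = 83.3% and 5/36 = 13.9%, against 80% and 20% printed.
- Pearson chi-square for 30/36 v 5/36: 72 × (30×31 − 6×5)² / (36×36×35×37) = 34.75, P = 3.8e-9. Fisher gives 3.5e-9. Both printed bounds are met, but identical counts give one P-value under one test, so two different bounds are unexplained.
- Cumulative reading (Good or better = 30, Perfect = 30): this leaves nobody at exactly Good, and still gives one P-value.

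**2. The abstract.** Among denominators from 30 to 44, only 35/38 and 23/36 give 92.1% and 63.9%. They total the 74 recruited, but Table 2 has 36 in group A.
- Pearson: 74 × (35×13 − 3×23)² / (38×36×58×16) = 8.69, P = 0.0032. Fisher 0.0043; Yates-corrected 0.0077. None is 0.012.
- In group B, Table 2 has 5 children (13.9%), or 10 (27.8%) if its rows are added. Neither is 63.9%, unless the abstract counts as satisfied a grade that Table 2 does not show.
- An unordered Pearson test on three grades could give 0.012. Its statistic is at least 8.69, so on 2 degrees of freedom P ≤ exp(−8.69/2) = 0.0130, and 38 whole-number splits round to 0.012. Across them the Mann-Whitney P runs from 0.004 to 0.053. No document says that this was done.

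**3. Why one grade has no direction.** Assume grades at 10/30/35/25% from lowest to highest, and a common odds ratio of 4 towards higher grades.
- Top grade: odds 0.25/0.75 × 4 = 4/3, so 57.1%.
- Top two grades: odds 0.60/0.40 × 4 = 6, so 85.7%.
- Second grade: 85.7 − 57.1 = 28.6%, down from 35%, although satisfaction has improved.

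**4. Power.** The documents give no grade list, target effect or power, so grade distributions and odds ratios are assumed. Simulation: 36 per arm, two-sided 0.05, common odds ratio, 1,500 trials per cell (error about 1.3 points). Entries are unordered Pearson v Mann-Whitney, in %.

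| Assumed group B grades (%) | Odds ratio 2.5 | Odds ratio 3 |
|---|---|---|
| 33/33/33 | 41.7 v 51.5 | 58.5 v 69.3 |
| 36/40/24 | 45.3 v 54.6 | 58.8 v 68.5 |
| 25/25/25/25 | 41.1 v 59.1 | 55.2 v 72.0 |
| 15/21/40/24 | 36.4 v 54.5 | 52.6 v 70.6 |
| 20/20/20/20/20 | 35.3 v 57.0 | 51.3 v 74.5 |

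The gap is 9 to 11 points with three grades and 17 to 23 with four or five. A separate set of 4,000 trials per scenario gave 10 to 12 and 17 to 24. Rounded, with room for simulation error: about 10, and 15 to 24. With two grades the tests are about equal (60% v 58% at odds ratio 3). Fisher on the second-highest grade alone had 2 to 7% power in these cells.

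**5. Error rate.** Two independent tests at 0.05 would give 1 − 0.95² = 9.75%. Two grades of one scale are not independent: with no true difference, the chance that either Fisher test was significant was 3.9 to 5.2%.

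**The case against.** The strongest reply is that lost power has not hurt the satisfaction result. The abstract's figures imply an odds ratio of (35×13)/(3×23) = 6.6, and Table 2's imply (30×31)/(6×5) = 31. At 6.5, in the same five scenarios, Pearson has 94 to 96% power against 98 to 99% for the rank test, and every printed P-value is below 0.05. Observed effects do not justify a choice of test, but this stands: no satisfaction effect is shown to have been missed. The number of grades is also unknown, and with two grades there is no order to lose.

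The reversal in step 3 is hypothetical, too. Both rows of Table 2 favour group A, so the printed P-values do not contradict each other in direction. That stands as well.

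A reader might infer that sedation went through Fisher or Pearson and lost power there. The documents do not support this. Sedation is never classed as categorical, its scale and test are not given, Figure 1 and part of the SAP were not available, and a sedation score could have gone through the Mann-Whitney test already in the plan. A reader might also infer that two P-values double the false-positive rate; step 5 shows no such inflation.

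Finally, the repeated counts may be a layout or copying slip. That would explain the duplicate row, but not the percentages or the differing P-values.

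**Conclusion.** The point holds for parental satisfaction. The plan names no ordered test for a graded outcome, Table 2 tests grades of one question separately, and the abstract adds a third P-value by an unstated method. The cost is clarity first. Power is lost only if the scale has three or more grades; the 10-point and 15-to-24-point figures rest on assumed grade distributions, a common shift and odds ratios of 2.5 to 3.

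It would go too far to say that the satisfaction conclusion is wrong or would change. The ordered test cannot be computed from what is printed. The faulty counts do mean that Table 2 cannot at present support any satisfaction P-value, and a change of test alone will not repair that. Whether sedation is affected is open.

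**What to change.** - List all satisfaction grades and tabulate them so that they sum to n in each arm. Correct the counts and percentages, and reconcile them with the abstract, including 38 v 36 in group A.
- Analyse satisfaction as one ordered variable: one tie-corrected Mann-Whitney test, with a proportional-odds ratio and 95% CI. Report one P-value and remove those for Good and Perfect.
- State the sedation scale and its test. If it has three or more levels and was tested with Fisher or Pearson, use the same ordered test.
- Keep Fisher for yes/no outcomes such as postoperative analgesia.

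The cost is one sentence in the SAP, a return to the case report forms for the counts, and a rerun in the same software. The downside is that the odds ratio assumes a common shift across grades; the rank test does not need that assumption.

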## Tables and Figure legends

**Table 1.** Demographic parameters of children with (group A) or without (group B) caudal block anesthesia.

[figure not shown]
Demographic parameters	Group A (n=36)	Group B (n=36)	P
Age (months), mean $\pm$ SD	20.68 $\pm$ 1.7	29,688 $\pm$ 3.4	0.3
Sex			
Female	16 (13%)	15 (11.25%)	0.5
Male	20 (15%)	21(15.75%)	
Heights (cm), mean $\pm$ SD	90 $\pm$ 2.08	103 $\pm$ 4,2	0.8
Weights (kg), mean $\pm$ SD	9 $\pm$ 1,05	12 $\pm$ 3,02	0.6

SD= standard deviation.

[figure not shown]
**Table 2.** Differences between children with or without caudal block anesthesia in the average pain scores at the various time points according to Children's Hospital Eastern Ontario Pain Scale (CHEOPS).

Variables	Group A (n=36)	Group B (n=36)	P
CHEOPS Score average	3 $\pm$ 0.11	5 $\pm$ 0.49	<0.005
At 30 minutes	2.6 $\pm$ 0.41	4 $\pm$ 0.44	<0.003
At 1 hour	2.11 $\pm$ 0.98	4 $\pm$ 0.54	<0.0001
At 2 hours	3 $\pm$ 0.44	4 $\pm$ 0.65	<0.003
At 6 hours	3.05 $\pm$ 1.53	4.80 $\pm$ 2.04	0.005

Postoperative analgesia	Yes	3.0 (8.3%)	36 (100%)	<0.001
	No	33 (91.7%)	0.0 (0.0%)	
Parental satisfaction	Good	30 (80%)	5.0 (20%)	<0.002
	Perfect	30 (80%)	5.0 (20%)	<0.001

**Figure 1.** Effect of caudal block versus non-caudal block anesthesia on pain intensity at 1 and 6 hours and the degree of sedation in children undergoing infra-umbilical surgery under general anesthesia.

**Figure 2.** Effect of caudal block versus non-caudal block anesthesia on movement score at 1 and 6 hours postoperatively in children undergoing infra-umbilical surgery under general anesthesia.

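### Table 2's CHEOPS average row gives group A a spread (± 0.11) too small for the four time points beneath it, if the row averages those scores and ± is SD

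*SAP*

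**What the plan says.** The title of Table 2 (SAP, Tables and Figure legends) announces "average pain scores at the various time points" on the CHEOPS. The top row, "CHEOPS Score average", has its own P value (<0.005). The five CHEOPS rows, with 36 children per group, are:

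| Row | Group A | Group B |
|---|---|---|
| Average | 3 ± 0.11 | 5 ± 0.49 |
| 30 minutes | 2.6 ± 0.41 | 4 ± 0.44 |
| 1 hour | 2.11 ± 0.98 | 4 ± 0.54 |
| 2 hours | 3 ± 0.44 | 4 ± 0.65 |
| 6 hours | 3.05 ± 1.53 | 4.80 ± 2.04 |

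Table 2 does not say what ± stands for. The Study population section says that data are reported as a mean with "standard deviation or median and interquartile range (IQR) according to distribution normality". Table 1 labels its own ± rows, for example "Heights (cm), mean $\pm$ SD". The available text does not say which times the average row covers or how they are weighted.

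**The concern.** The natural reading is that the top row averages, for each child, the four scores listed below it. On that reading its mean and spread are constrained by those rows. Group A's 0.11 is about a quarter of the smallest SD listed for that group (0.41), which is more shrinkage than averaging four scores from the same child would normally produce.

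The row is the table's only overall CHEOPS summary. A reader who takes 0.11 as an SD, for a meta-analysis or a later sample-size calculation, would badly overstate the precision in group A.

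**Working it through.** **Inputs.** The means and ± values are those of Table 2, with ± taken as SD and n = 36 per group. The within-child correlation ρ between time points is not given, so it is an assumption and is shown as a range.

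**1. Smallest SD for group A over all weightings, ρ ≥ 0.** For non-negative weights summing to 1, the SD of the average at ρ = 0 is smallest with inverse-variance weights, where it equals 1/√Σ(1/s²). Positive correlation can only raise it.

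- Σ(1/s²) = 1/0.41² + 1/0.98² + 1/0.44² + 1/1.53² = 5.95 + 1.04 + 5.17 + 0.43 = 12.58
- Smallest SD = 1/√12.58 = 0.282
- With every printed SD at its lower rounding limit the figure is 0.279.
- The printed 0.11 is smaller by a factor of 0.282/0.11 = 2.6.

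**2. Equal weights, group A.** SD = √[Σs² + ρ((Σs)² − Σs²)]/4, with Σs² = 3.663 and (Σs)² = 3.36² = 11.290.

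| Assumed ρ | SD |
|---|---|
| 0 | 0.48 |
| 0.3 | 0.61 |
| 0.5 | 0.68 |
| 0.8 | 0.78 |

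These are 4 to 7 times the printed value.

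**3. What would produce 0.11.** With a common correlation and equal weights, ρ = (16 × 0.11² − 3.663)/(11.290 − 3.663) = −0.455, beyond the limit of −1/3 for four equally correlated scores. At the most favourable weights a common ρ of about −0.29 is enough. Unequal correlations are not bound by −1/3. With equal weights and no restriction on correlation the SD can even fall to zero, because 1.53 is less than 0.41 + 0.98 + 0.44 = 1.83. To show how strong the cancellation must be, suppose that the three earlier scores are mutually uncorrelated. Their sum has SD √(0.41² + 0.98² + 0.44²) = 1.15. The 6-hour score would then need a correlation with that sum of (16 × 0.11² − 1.322 − 2.341)/(2 × 1.15 × 1.53) = −0.99.

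**4. Reading ± as a standard error.** For the average row alone, group A's 0.11 × √36 = 0.66 is compatible with step 2. Group B's 0.49 × 6 = 2.94 is not, because no weighted average can have an SD above the largest component SD, which is 2.04. If all five rows were standard errors, every figure would scale by 6 and the gap in step 1 would remain.

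**5. Group B.** The smallest SD by the step 1 formula is 1/√11.20 = 0.299, so 0.49 is not excluded. Taken as exact, the mean of 5 exceeds every listed score (maximum 4.80), and equal weights give (4 + 4 + 4 + 4.80)/4 = 4.20. But the three entries of 4 may be whole-number roundings. At ρ ≥ 0 an SD of 0.49 limits the 6-hour weight to 0.210, so those entries must average at least (4.5 − 0.210 × 4.80)/0.790 = 4.42 for the row to round to 5. That lies within the rounding range. The printed 5 ± 0.49 is therefore attainable.

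**6. Group A's mean.** Equal weights give (2.6 + 2.11 + 3 + 3.05)/4 = 2.69, which rounds to 3. There is no discrepancy here.

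**The case against.** The strongest objection is to the premise. Nothing states that the row is a within-child average of the four rows below it. The table title can equally mean group means at each time rather than an average across times. The row stands above the 30-minute row with its own P value, so it could be a separate assessment or include a time that is not listed. The available SAP text is also incomplete. All of this stands, and it makes the finding conditional. It does not make the row interpretable as printed.

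The SD reading is also not fully secure. The SAP gives a general format and does not mention Table 2, and Table 1's labels are weak support. Reading its group B age as 29.688, an SD reading gives t = (29.688 − 20.68)/(√(1.7² + 3.4²)/6) = 9.008/0.634 = 14.2, beside a printed P of 0.3. The SD reading here therefore rests on the SAP's stated format. The standard-error alternative fails for the reasons in step 4.

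A reader might go further and infer that the row is arithmetically impossible, that group B's mean is an error, or that the apparent difference of 2 points is inflated. The documents support none of these. Negative correlations can give 0.11, and rounding can give 5 ± 0.49. If both means are whole-number roundings, their difference could be anything from 1.0 to 3.0. Nor is the P value shown to be wrong: the SAP's Mann-Whitney test works on ranks and cannot be checked from means and SDs.

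**Conclusion.** The point holds for one figure, group A's ± 0.11. It rests on three assumptions: the row averages each child's scores over the four listed times with non-negative weights, ± is SD throughout, and within-child correlations are zero or positive. Under these, the printed value is at least 2.6 times too small. Without the third it is implausible rather than impossible. Group B's row is supporting evidence only.

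The consequence is limited. All four listed time points favour group A, the abstract does not quote this row, and no change in the direction or size of the effect is claimed. Severity: minor.

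**What to change.** Recompute the row from the case report form data as each child's average over stated time points and weights. Replace its means, SDs and P value, using the Mann-Whitney test that the SAP already specifies. List any further time point that enters the average. If the row is instead a separate assessment, say so and verify group A's 0.11 against the data. In either case, label ± in Table 2 as SD or SE.

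The cost is one recalculation from data already held and a table label. The downside for the authors is that group A's spread will probably be larger than printed.
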